To determine the required sample size, the sample size calculation was based on a two-sample test for proportions. Results indicated that 354 participants per group, 708 participants in total, will allow a difference in proportions in the need for a GA from 25% to 15% to be detected with 90% power and a two-sided significance test at the 0.05 level. We anticipate that at least 10 clinics who are providing care under Child Friendly dental pathway and 10 clinics who are providing care under the usual Specialist Dental pathway will participate in the study.

The study sites are divided into two groups: Community Dental Services (CDS) and Child Friendly Dental Practices (CFDP) with an original planned sample size of 708 participants from both groups, or 354 per group **at the end of the study**. Due to low recruitment numbers from the CFDP group among the study sites, the remainder of the required sample size for the CFDP group will be supplemented with unconsented, **anonymised** data obtained from the dental referral management system, **the data will be from a similar timeframe** of the consented data collected in the CDS group obtained from the study sites.

In 2023, 230 patients were seen and treated within CFDP if the same number are seen and treated within 2024 this will provide data on 460 patients. As we would have a larger sample from the CFDP this would mean only 292 patients would need to be recruited from the CDS to reach a power of 90% to detect a difference in proportions in the need for a GA from 25% to 15%. This approach will allow the study to meet its target sample size and effectively address the research questions and objectives. Recruitment and numbers seen through CFDP will be closely monitored so that recruitment can end as soon as the minimum sample size is reached.

Inclusion / exclusion characteristics

Child aged 4-15 years only (cut-off 16th birthday)

Child resident in Greater Manchester

Child referred by general dental professional based in Greater Manchester

Child contact information complete i.e., age, contact address, telephone number, carer

Extractions requested and radiograph provided

Child medical history complete

Reason why treatment cannot be provided by referring dentist provided

Dental charting complete

Child with no or mild medical complexities

Child with no or mild behavioural complexities

Child presents with symptomatic teeth in one or two quadrants only

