Primary: The primary outcome, measures whether a child has had a dental extraction under General Anaesthetic two years after referral as indicated in electronic patient records (recorded through HES data or through CDS patient records).

Secondary: The secondary outcomes to be considered in this project include:

- Waiting time until first appointment
- Number of sessions of treatment
- Whether a child was successfully seen and treated. For this outcome success is defined as treatment completed by a dentist that results in a child being referred back to their own dentist or discharged, pain free.
- The number of extractions and restorations as reported in NHS BSA data
- The courses of antibiotics taken during wait and treatment
- Participants referred back into the specialist pathway within two years of referral.
- Dental pain experienced by a child
- Participants views of their treatment and engagement with the dental profession (follow up of dental appointment) as indicated by the responses to the text message. Questions will include an adapted version of the NHS Friends and Family Test, questions on satisfaction, possible negative/adverse experiences, possible positive experiences, and an option for free text comments at the end of the survey.

Qualitative work will focus on two groups: (a) dental professionals (incl. triage, in-practice dental teams, CDS teams and referring practices) and (b) patients (incl. parents and children) accessing and using CFDPs.

(a) Dental teams' attitudes and beliefs regarding CFDP will be examined to better understand what worked well, what created barriers and look at how best to support implementation for such initiatives if they become routine practice.

In a qualitative approach, we will explore dental team beliefs, attitudes, and opinions regarding CFDPs and traditional pathways. To allow for the realist evaluation to take place, a combination of focus groups and one-to-one interviews will take place with the triage team and staff at CFDPs.

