Summary descriptive data will be reported by study arm and overall using tables of frequencies or means and standard deviations as appropriate to characterise the population and identify any imbalance between groups. The comparison of outcomes from the traditional specialist dental service route (control) compared to the intervention treatment under the alternative Child-Friendly Dental Practice will be assessed to determine if there are clinically meaningful and statistically significant differences in key outcomes. The primary outcome is receipt of GA for tooth extraction within two years of initial referral. Referral along both pathways may still result in the need for a GA for some children but a key metric will be to determine whether there

is a meaningful difference in the number of GAs per referral pathway. The primary outcome will be analysed using a mixed effects logistic regression model, accounting for the traditional specialist dental service route or alternative Child-Friendly Dental Practice, with random effects for centre. An adjusted logistic regression analysis additionally accounting for the age, deprivation, ethnicity, sex of the child along with the number of teeth requiring treatment at initial examination (through the CFDP or CDS) will also be undertaken. The analysis dataset will include all participants for whom there is follow-up data from the NHS BSA and the baseline covariates.

Analysis of secondary outcomes will be undertaken in a similar manner using covariate adjusted linear or logistic regression models as appropriate, we will include the modifying effect of deprivation

The health economics analysis will adopt a cost-consequences approach whereby the costs of each pathway will be presented separately but alongside relevant outcomes: 1) dental extractions under GA, 2) count of children who are successfully seen and treated in each pathway, 3) count of treatments performed (extractions, restorations), 4) mean wait time and 5) dental pain experienced by a child. Resource use and costs from the CFDP pathway will also be used in a budget impact analysis. Differences in outcomes will be generated from the quantitative analysis.

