Appendix A – Gantt Chart

APPENDIX B – Data collection

Data collected through CDS

ID	Contract Number	Provider Name	Locality	Month of Submission to Dental Comm Team	Practice patient code	Pt Age (in years)	Patient Postcode	URN	Referring Practice Name	Referring GDP Name	Referring Practice Postcode	Number of courses of Antibiotics whilst waiting?

Date of Referral	Appt made? (Yes / No)	Reason no appt (Please select from the drop down)	Number of appts attended	Number of appts WNB	Bitewings taken?	Date of Initial Appointment	Number of decayed teeth needing treatment *at CDS	Outcome (please select from drop down)

Treatment Provided								Notes	Who carried out treatment	Previously seen at CFDP or other services after referral	GM central emergency system (Out of hours) Y/N
Number of Filling(s)	Number of Extraction(s)	Number of Stainless Steel Crowns (SSCs)	Number of Temp Fillings	Fluoride Varnish Application (Y/N)	Silver Diamine Fluoride (SDF) (Y/N)	Oral Health Improvement Advice Given (Y/N)	Antibiotics (Yes / No)				

Data collected through CFDP

ID	Contract Number	Provider Name	Locality	Month of Submission to Dental Comm Team	Practice patient code	Pt Age (in years)	Patient Postcode	URN	Referring Practice Name	Referring GDP Name	Referring Practice Postcode

Number of courses of Antibiotics whilst waiting?	Date of Referral	Appt made? (Yes / No)	Reason no appt (Please select from the drop down)	Date of Initial Appointment	Number of appts attended	Number of appts WNB	Bitewings taken?	Number of decayed teeth needing treatment
			Cannot contact					

Treatment Provided								Outcome (please select from drop down)	Notes	Who carried out treatment	GM central emergency system (Out of hours) Y/N	Patie
Number of Filling(s)	Number of Extraction(s)	Number of Stainless Steel Crowns (SSCs)	Number of Temp Fillings	Fluoride Varnish Application (Y/N)	Silver Diamine Fluoride (SDF) (Y/N)	Oral Health Improvement Advice Given (Y/N)	Antibiotics (Yes / No)					

NHS BSA data headings

Link	Flagged (linked or not linked data set 0 = not linked, 1 = linked)
PANDA_ID	PANDA ID (include if linked)
PATIENT_ID	Patient ID (random number generated by NHS BSA for each patient)
Age of Pt at every CoT	age of Pt at every CoT (will need to use DOB and treatment date)
GENDER	Gender
PT_LSOA	Lower Super Output Area of patient's home address at time of treatment

IMD	UoM will supply this as a post-code lookup. IMD against NEPU 2019 scores an
IMD rank	

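### One analysis dataset requires the baseline covariates, so children with known GA status are dropped from a primary model that uses none of those covariates

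*Protocol*

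**What the plan says.** Section X describes two models for the primary outcome. The first is the primary one: "The primary outcome will be analysed using a mixed effects logistic regression model", containing pathway and random effects for centre. The second adds child-level covariates: "An adjusted logistic regression analysis additionally accounting for the age, deprivation, ethnicity, sex of the child". It also includes a tooth count, which is taken when either service first examines the child, and it is presented as an extra analysis. The next sentence defines the data to be analysed: "The analysis dataset will include all participants for whom there is follow-up data from the NHS BSA and the baseline covariates". No other analysis set is defined, and the protocol says nothing else about missing covariates.

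The outcome does not depend on any covariate. Under Outcomes, the primary outcome is a dental extraction under GA within two years of referral, "as indicated in electronic patient records (recorded through HES data or through CDS patient records".

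In Appendix B, the CDS and CFDP forms both ask whether an appointment was made and then give a field "Reason no appt (Please select from the drop down". The listed fields include age, gender, small-area code and deprivation index, but not ethnicity.

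The Sample size section gives an "original planned sample size of 708 participants from both groups", and then an alternative of 460 CFDP and 292 CDS children. Both are stated to give 90% power for 25% against 15%. The cover sheet and that section treat 708 as the number needed at the end of the study, and recruitment may stop once the minimum is reached. No allowance for incomplete records is given.

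**The concern.** The rule is a stated complete-case condition on five covariates: age, deprivation, ethnicity, sex and tooth count. It applies to a model that contains none of them. This is more than a detail left to the SAP, because a SAP that kept every child with known GA status would depart from the protocol's sentence.

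Two things are at stake. The first is precision: the 90% power is calculated on all children, but the primary model would be fitted only to those with complete covariates. The second is the population. The outcome clock starts at referral, whereas the tooth count is recorded at a later examination. Any referred child who is never examined cannot have that value and would leave the primary comparison because of something that happened after referral.

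**Working it through.** **1. Reproduce the plan's figure.** Inputs from the Sample size section: 25% against 15%, two-sided 0.05, power 90%. The pooled two-proportion formula is

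n = [1.96 × √(2 × 0.20 × 0.80) + 1.2816 × √(0.25 × 0.75 + 0.15 × 0.85)]² / 0.10² = 334.2.

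With continuity correction, n/4 × [1 + √(1 + 4/(n × 0.10))]² = 353.9, so 354 per group. This matches the protocol exactly. For 460 to 292 (ratio 1.575) the same method needs 287 CDS children, close to the stated 292. The plan's arithmetic is not in dispute.

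**2. Power at the planned numbers.** Power = Φ{[0.10 − ½(1/n₁ + 1/n₂) − 1.96 × SE₀] / SE₁}, where SE₀ is the pooled and SE₁ the unpooled standard error.
- 354 + 354: (0.09718 − 1.96 × 0.03007) / 0.02983 = 1.282, power 90.0%.
- 292 + 460: (0.09720 − 1.96 × 0.02928) / 0.03032 = 1.313, power 90.5%.

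**3. Which covariates can be missing.** Complete contact information, including age and address, is an eligibility condition in the Sample size section's list of inclusion characteristics. The NHS BSA fields in Appendix B hold age, gender, small-area code and deprivation index. Age, sex and deprivation should therefore be nearly complete. That leaves tooth count (needs an examination) and ethnicity (no listed field).

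**4. Loss under the rule.** The protocol gives no rate, so a range is assumed. With tooth count and ethnicity each missing independently in a share m of children, the share kept is (1 − m)².

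| m (assumed) | Share kept | CDS + CFDP kept | Power |
|---|---|---|---|
| 0 | 100% | 292 + 460 | 90.5% |
| 2% | 96.0% | 280 + 442 | 89.3% |
| 5% | 90.3% | 264 + 415 | 87.4% |
| 10% | 81.0% | 237 + 373 | 83.5% |

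These figures ignore clustering by centre. If the primary model keeps every child with known GA status, covariate gaps do not reduce the 90.5%.

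**5. Possible bias, if unexamined children are in the cohort.** Assume the CFDP GA proportion among all referred children is 15%, that 10% are never examined, and that these have GA risk g. The proportion among those kept is (0.15 − 0.10g) / 0.90.

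| g (assumed) | CFDP proportion analysed | Difference from 25% |
|---|---|---|
| 5% | 16.1% | 8.9 points |
| 15% | 15.0% | 10.0 points |
| 25% | 13.9% | 11.1 points |
| 40% | 12.2% | 12.8 points |

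The shift can go either way and is zero when the risks are equal.

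**6. Whether they are in the cohort.** The protocol points both ways. The recruitment text in section V and the Data handling section describe the referral-system extract as covering all eligible children, with no requirement to attend. The Sample size section derives 460 from children who had been seen and treated (230 × 2), and Planned interventions defines the exposed cohort by triage and treatment through the new pathway.

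**The case against.** **Scope of the sentence.** It directly follows the description of the adjusted model, and the only covariates it can mean are those just listed. It may have been intended for that model alone. This is a fair reading, but the text speaks of one analysis dataset and defines no other. If the narrower meaning was intended, the same edit is needed to say so.

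**A common sample is a legitimate choice.** Fitting both models to the same children means that a change in the estimate reflects adjustment and not a change of sample. This stands, and the fix keeps that comparison as a sensitivity analysis. It does not justify discarding known outcomes from the primary model.

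**Stronger readings that the protocol does not support.**
- A reader might infer that the rule cuts 460 + 292 by removing CFDP children who were never examined. The 460 is a count of children already seen and treated, so this is not shown.
- A reader might infer that the rule makes CFDP look better, because unexamined children return to specialist care for a GA. The only no-appointment reason visible on the CFDP form is failure to make contact, and such families could have fewer GAs or more.
- Applying equal missingness to all five covariates gives a more alarming result: at 10% each, 0.90⁵ = 59% of children remain and power is 69.9%. That is implausible given step 3 of the working.

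**A shortfall is not certain.** The referral-system extract begins in January 2022, while the 460 counts only 2023 and 2024, so there may be spare CFDP numbers. Appendix B may also not be exhaustive, since Data handling says the sources are not limited to those named, and ethnicity may come from elsewhere. Both points limit the size of the concern, but neither removes the mismatch between the rule and the model.

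**Conclusion.** The point holds as a fault in the rule for the analysis set. Followed as written, section X removes children with known GA status from a primary model that needs none of the values they lack. On an assumed 5% missing for each of tooth count and ethnicity, independently, about one child in ten is lost and power at 460 + 292 falls from 90.5% to about 87%. At 2% to 10% each, it falls to between 89% and 83%. These figures rest on assumed rates and ignore clustering.

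Bias is a conditional second consequence. It arises only if unexamined referred children belong to the cohort and their GA risk differs from that of examined children. The protocol contradicts itself on the first condition and is silent on the second, so neither a size nor a direction can be claimed. If the risks are equal, only power is lost.

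The same sentence also requires NHS BSA follow-up although GA status comes from HES or CDS. That is a separate matter, and this conclusion does not depend on it.

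**What to change.** Replace the analysis-dataset sentence in section X so that:
- the pathway-and-centre model includes all eligible children with ascertained GA status, whatever their covariates;
- the covariate condition applies to the adjusted model only;
- missing covariates in the adjusted model are handled by multiple imputation, with an imputation model containing pathway, GA, centre and referral-form fields such as the dental chart and complexity score (Appendix B), which are available before any CFDP or CDS examination;
- the adjusted model on complete cases is a sensitivity analysis, with the unadjusted model fitted to those same children, so that the effect of adjustment can be separated from the change of sample.

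The protocol should also state whether referred children who were never examined belong to the cohort. Changing the analysis-dataset sentence does not settle that question.

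The cost is one reworded rule, one clarification of the population and some extra analysis. No new data collection is needed. The price is reliance on a missing-at-random assumption in the adjusted model, which is hardest to defend for the tooth count of a child who was never examined. The referral-form fields make it more plausible, and the complete-case results show how much depends on it.

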Before Covid-19 children in Greater Manchester were already experiencing waiting times of up to 12 months for dental treatment under GA, often leading to episodes of pain, time off school and repeat courses of antibiotics. According to the Commissioners within GM as of December 2021, there were 1779 children on the waiting list, 716 of whom have been waiting over 52 weeks. These figures show the continued pressure on the system with children waiting an unacceptably long time for treatment. These numbers are now decreasing with the implementation of CFDP, where this pathway is able to take new patients entering the referral system. The CFDPs have shown promising preliminary results with 50% of children seen within a CFDP. The dental commissioning team in GM are committed to increasing the number of CFDPs by reallocating existing funding. There is considerable interest in this type of scheme from other areas of the country in view of the national policy drivers supporting flexible commissioning; following the work in GM further regional pilots have been established this year (for a minimum of 6 months) in the South East of England lead by [name] (who has agreed to join our steering committee if the study is funded – further information is available in the letter of support from [name]). There has also been interest in our research proposal from Northern Ireland and Wales.

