End of the study will occur when data is collected from NHS parties and there is no longer a requirement for CAG Support (section 251 support is closed down) for the legal basis of processing collected data.

V. PARTICIPANTS

Study population

Children with dental decay referred and triaged through the paediatric referral system who all meet eligibility criteria to be seen by a CFDP.

And

Individuals who work or are connected to the paediatric referral system (dentist, dental team , triages and stakeholders)

Inclusion and exclusion criteria

Inclusion criteria:

- Paediatric patients (aged 4 to 16 years old) referred through the Greater Manchester dental referral system and who have been triaged as appropriate for treatment at a CFDP.
- Patients with parents/guardians who have the capacity to consent through the study sites or unconsented cohort from the dental referral management system subject to CAG Approval.

Exclusion criteria:

- Patients referred for orthodontic treatment
- unconsented cohort who opts out of having their confidential data used for research purposes through the national and study specific opt-out service

Setting and sampling

The study sites are located across Greater Manchester and therefore the study will encompass a diverse range of sites with equivalent Community Dental Service clinics recruiting patients from a similar geographic area. Given the diversity within Greater Manchester the study will be able to recruit from a diverse and representative cohort. Participants will be assessed for inclusion into the study by the specialist triage according to inclusion and exclusion criteria.

Screening, Selection and Recruitment of Subjects

Children who attend either CFDP or CDS if they meet the eligibility criteria (or have been triaged as appropriate to be seen within a CFDP) they can be recruited into the study via the CDS or CFDP (a member of staff at the CDS or CFDP). If patients have already been seen and treated within a CFDP or CDS but are still eligible to be recruited a letter will be sent from the dental team at the CDS or CFDP.

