- Secondary care resource use: dental extractions under GA. Data collected from routine data: HES and CDS software
- Intervention resource use for CFDP pathway: additional costs paid to deliver the pathway (as outlined in the service level agreement) and additional costs in terms of setting up the pathways (providing training and resources/support for dentists. Data collected from CFDP providers and commissioners.

Unit costs will be attached to dental treatments via the dental treatment band and the associated Units of Dental Activity cost. Unit costs for prescribed antibiotics will be obtained from Prescriptive Cost Analysis data (21). Unit costs for secondary care resource use are sourced from the Healthcare Resource Group tariffs for tooth extractions(22).

Intervention costs will be attached data from CFDP providers and commissioners using salary costs from Unit Costs of Health and Social Care (23). The cost per patient for each pathway will be summarised and presented adjusted for inflation.

The health economics analysis will adopt a cost-consequences approach whereby the costs of each pathway will be presented separately but alongside relevant outcomes: 1) dental extractions under GA, 2) count of children who are successfully seen and treated in each pathway, 3) count of treatments performed (extractions, restorations), 4) mean wait time and 5) dental pain experienced by a child. Resource use and costs from the CFDP pathway will also be used in a budget impact analysis. Differences in outcomes will be generated from the quantitative analysis.

The analysis will take an NHS perspective with a 2 year time horizon. Longer term costs and outcomes will not be modelled due to the need for treatment being acute and focusing on child teeth. This approach will provide dental service commissioners with appropriate health economic data to inform future commissioning decisions related to CFDP.

VII. Monitoring of the study

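### As written, waiting time to first appointment would in effect be compared only among children already seen, and the two pathways' children enter by different rules

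*Protocol*

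**What the plan says.** The Outcomes section lists "Waiting time until first appointment" among the secondary outcomes. Section X (Data analyses) gives the method for all of them: "Analysis of secondary outcomes will be undertaken in a similar manner using covariate adjusted linear or logistic regression models as appropriate". It also sets costs beside five outcomes that include "4) mean wait time and 5) dental pain experienced by a child"; the Cost effectiveness section repeats the list. No time-to-event method is named for any outcome.

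Section X says of the analysis set: "The analysis dataset will include all participants for whom there is follow-up data from the NHS BSA and the baseline covariates". One covariate is the "number of teeth requiring treatment at initial examination (through the CFDP or CDS").

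Entry differs by source. Under Screening, Selection and Recruitment, consent is sought from "Children who attend either CFDP or CDS if they meet the eligibility criteria", or by letter from children already seen and treated. The same section plans a referral-system extract of every eligible child from January 2022 to December 2024. The Sample size section uses that source to make up the CFDP group, from a timeframe similar to that of the consented CDS data. It does not say whether referral dates or attendance dates must match.

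Appendix B records, on both the CDS and the CFDP form, the referral date, whether an appointment was made, the reason if not, and the date of the initial appointment.

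**The concern.** Waiting time has no value until the child is seen. If only seen children are analysed, inclusion depends on the outcome itself: the longer the wait, the less likely the child is to be counted. The analysis would then describe how long children waited who had been seen by some date, not how long a child referred down a pathway waits.

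This matters because shorter waits are a stated patient benefit (Risks and benefits), and mean wait is one of five outcomes that commissioners will read beside the costs. If one pathway is slower, its mean is pulled down further and the contrast shrinks. If the pathways also enter children by different rules, part of any difference in waits reflects those rules and not the service.

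**Working it through.** **Step 1: follow one unseen child through the text.** The child is eligible and referred in autumn 2024, with no first appointment at data retrieval (June to August 2025 in the timescale).
- Linear model: no outcome value. A logistic model does not fit a duration.
- Covariates: no initial examination, so no count of teeth requiring treatment.
- Cost-consequence table: no contribution to a mean wait.
- Consented cohort: never enrolled, because entry is at or after attendance.
- Referral-system extract: present, but lost at the steps above.

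**Step 2: size.** The protocol states no waiting-time figure, so there is none to reproduce. The following inputs are assumptions: true mean waits of 12 and 3 months; gamma-distributed waits with shape 1 (exponential) or 3; uniform referral dates. The dates come from the protocol: extract window January 2022 to December 2024, recruitment May 2023 to December 2024, retrieval ending August 2025.

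Exponential waits with mean *m* = 12, referrals over 36 months, cut 8 months after the last referral. The time available, *u*, is uniform on 8 to 44 months.
- Unseen share = (*m*/36)(e^(−8/*m*) − e^(−44/*m*)) = (12/36)(0.5134 − 0.0256) = 0.163.
- Mean of wait × (seen) = *m* − (*m*/36)[(8 + 2*m*)e^(−8/*m*) − (44 + 2*m*)e^(−44/*m*)] = 12 − (12/36)(16.43 − 1.74) = 7.10.
- Seen-only mean = 7.10/(1 − 0.163) = 8.48, and 1 − 8.48/12 = 29% low.

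The other rows use the same principle, by numerical integration. Each pair is shape 1, then shape 3:

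| Entry rule | Seen-only mean, true 12 | Understated | Seen-only mean, true 3 |
|---|---|---|---|
| Sampled at attendance May 2023 to Dec 2024, referrals back to late 2020 | 10.45; 11.86 | 13%; 1% | 3.00; 3.00 |
| Referrals Jan 2022 to Dec 2024, cut Aug 2025 | 8.48; 10.69 | 29%; 11% | 2.94; 3.00 |
| Referrals Jan 2022 to Dec 2024, cut Dec 2024 | 7.31; 10.04 | 39%; 16% | 2.73; 2.91 |
| Referrals May 2023 to Dec 2024, cut Dec 2024 | 5.04; 7.94 | 58%; 34% | 2.48; 2.82 |

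In the second row, 16.3% and 13.5% of children with a true mean of 12 are unseen, against 0.6% and under 0.1% with a true mean of 3. A true difference of 9 months shows as 8.48 − 2.94 = 5.5 (shape 1) or 10.69 − 3.00 = 7.7 (shape 3). In the first row it shows as 7.45 or 8.86.

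**Step 3: what drives the size.** In every row, the longer wait is understated by more. The entry rule matters as much as the wait. With attendance sampling in a steady state and unlimited look-back, the seen-only mean is right for children who are eventually seen; only those never seen are missing.

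**The case against.** The strongest reply is that the protocol never says waits are analysed only among seen children. It does not assign waiting time to linear regression by name, and handling of unseen children can be left to an analysis plan that is not shown. The first part is true: the restriction is an inference from the model classes, the covariate and the entry rule. But the choice left open is between two model classes, neither of which can hold a child still waiting, and the mean is named outright. That is a method fixed badly rather than a detail left open.

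A second reply also stands in part. Among consented CDS children the regression drops nobody, because unseen children were never enrolled, and a Cox model on the same attenders would have nobody to censor. The cohort definition must change along with the model.

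Stronger readings that a reader might infer, and that the documents do not support:
- *The difference between pathways is roughly halved.* A true 9 months shows as 7.31 − 2.94 = 4.4 (51% low) only with exponential waits, a January 2022 referral floor and a December 2024 cut for CDS, and an August 2025 cut for CFDP. The protocol sets no referral floor for consented children.
- *CDS is the slower pathway, so the CFDP benefit is understated.* No first-appointment wait is given for either pathway.
- *The waiting list proves waits of this length.* The protocol reports that "there were 1779 children on the waiting list, 716 of whom have been waiting over 52 weeks" (716/1779 = 40%). This is a December 2021 list, in a paragraph on waits for treatment under GA, and the protocol says the numbers are falling. It is context only.
- *Unseen CDS children cannot be recorded.* The CDS form has fields for no appointment and its reason.

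**Conclusion.** The point holds in this form. Followed as written, the waiting-time comparison selects children on the outcome and sets side by side two groups that enter by different rules. A seen-only mean tends to be too low, and more so where waits are longer.

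The size cannot be read from the protocol. For an assumed true mean of 12 months it is about 1 to 13% under attendance sampling with referrals reaching back to late 2020, and 11 to 29% under a referral window of January 2022 to December 2024 with an August 2025 cut. It is larger only under stricter cut-offs. For an assumed mean of 3 months it is at most about 2% in those two settings. These ranges rest on the assumed means, the gamma shapes and uniform referral dates. Which pathway is favoured is unknown.

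This is one secondary outcome and leaves the primary GA comparison untouched. It is worth correcting because commissioners will see it beside costs and most of the data needed are already planned.

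**What to change.** For the waiting-time outcome only:
1. Define the cohort in both pathways by one referral-date window, using the planned extract of all CFDP-eligible children and the form fields for referral date, appointment status and initial appointment date.
2. Analyse time from referral to first appointment as time-to-event, with a centre effect. Censor children still waiting at the data cut. Treat leaving the list without an appointment (for example, a family that could not be contacted) as a competing event.
3. Leave the initial-examination tooth count out of this model.
4. Beside the mean wait in the cost-consequence table, report the percentage seen by fixed times and a restricted mean wait. Take the horizon no further than every included referral has reached by the data cut. Referrals to December 2024 with an August 2025 cut allow about 8 months; closing the window earlier allows a longer horizon.
5. If unseen CDS children cannot be identified, apply the same entry rule in both arms and state that the result describes waits among children seen. Restricting to older referrals alone does not cure the problem: with exponential waits of mean 12 months, e^(−18/12) = 22% are unseen at 18 months, and (12/18)(e^(−1.5) − e^(−3)) = 12% across referrals 18 to 36 months old.

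The cost is protocol wording, a little more analysis, and a restricted summary that is less simple to explain than a mean.
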